8. IMMUNOGENICITY EVALUATION

Immunogenicity data summaries and analysis for primary and secondary endpoints will be presented for the mITT population, which is the primary population for analysis. The Per Protocol population displays will be generated only if >10% of subjects are found to have data excluded from a primary or secondary timepoint. Immune responses in terms of strain-specific 2013 and 2017 A/H7N9 HAI and Neut antibody titers will be summarized by study group at each time point. Descriptive summary statistics will be provided for all assays and time points including number of subjects with non-missing results, percentage of subjects with titers $\geq 1:40$, percentage of subjects achieving seroconversion, and GMTs along with corresponding 95% CI. Exact confidence intervals will be presented for proportional endpoints. Summaries of primary and secondary immunogenicity endpoints are presented for the 2013 A/H7N9 strain in [Table 24](#), [Table 25](#), [Table 26](#), and [Table 27](#) and for the 2017 A/H7N9 strain in [Table 28](#), [Table 29](#), [Table 30](#), and [Table 31](#).

Reverse cumulative distribution (RCD) curves will be presented for post-vaccination HAI and Neut antibody titers. Plots for each assay will be generated with 3 columns (Day 22 post vaccination 1, Day 22 post vaccination 2, and Day 181 post vaccination 2) and 2 rows (2013 A/H7N9, 2017 A/H7N9), and separate curves within each panel for each study group, as shown in [Figure 2](#), [Figure 3](#), [Figure 4](#), and [Figure 5](#).

Figures depicting the HAI and Neut GMT over time will also be presented as shown in [Figure 6](#), [Figure 7](#), [Figure 8](#), and [Figure 9](#) for both 2013 and 2017 A/H7N9 strains.

The spearman correlation between HAI and Neut antibody titers will be calculated at each time point over all groups. The correlation will be depicted in scatter plots as [Figure 10](#) and [Figure 11](#) for both the 2013 and 2017A/H7N9 strain.

Individual HAI and Neut assay results will be provided in [Listing 9](#).

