[Implementation Note: A generic sample figure is shown below. The scatter plots should be presented in a seven figure files (one for each study group, and one for overall) each with 8 separate panels (4 columns for each visit (Baseline, Day 22 post vaccination 1, Day 22 post vaccination 2, and Day 181 post vaccination 2) and 2 rows for the strains (A/Shanghai/2/2013 (A/H7N9), A/Hong Kong/125/2017 (A/H7N9))). Visit labels should be included in the panel header. Within each panel distinct marker types and colors should be used to indicate the study groups, with study group labels included in a legend. Each study group should have a unique color and marker shape used within its individual figure file. The spearman correlation should be calculated over all subjects and annotated within each panel as “Spearman Correlation (r=0.xx, p=0.xx)”]

[figure not shown]

[figure not shown]
Figure with Similar format:

Figure 11: Correlation of Hemagglutination Inhibition Antibody and Neutralizing Antibody by Study Day and Study Group, Per Protocol Population

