[Implementation Note: A generic sample figure is shown below. The scatter matrix should be presented in a single figure with as shown below. Within each panel distinct marker types and colors should be used to indicate the study groups, with study group labels included in a legend. Each study group should have a unique color and marker shape. The spearman correlation should be calculated over all subjects an included in the top-right diagonal as “Spearman Correlation (r=0.xx, p=0.xx)” A legend will include the axis units. The Scatterplot matrix will be repeated twice in the same figure file for HA and NA specific ASC expression.]

Figures with similar format:

- Figure 19:** Correlation of A/Shanghai/2/2013 (A/H7N9)-Specific Antibody Secreting Cells by Immunoglobulin Type at Day 8 Post Vaccination 2, Per Protocol Population
- Figure 20:** Correlation of A/Hong Kong/125/2017 (A/H7N9)-Specific Antibody Secreting Cells by Immunoglobulin Type at Day 8 Post Vaccination 1, Per Protocol Population
- Figure 21:** Correlation of A/Hong Kong/125/2017 (A/H7N9)-Specific Antibody Secreting Cells by Immunoglobulin Type at Day 8 Post Vaccination 2, Per Protocol Population
- Figure 22:** Correlation of A/Shanghai/2/2013 (A/H7N9)-Specific Antibody Secreting Cells at Day 8 Post Vaccination 1 with Antibody Response at Day 21 Post Vaccination 1, Per Protocol Population

[Implementation Note Update: The scatter matrix should be presented in a single figure with one column for each Immunoglobulin type (IgM, IgG, IgA) and one row for each antibody titer (HAI, Neut). Within each panel distinct marker types and colors should be used to indicate the study groups, with study group labels included in a legend. Each study group should have a unique color and marker shape. The spearman correlation should be calculated over all subjects an included in the top-right diagonal as “Spearman Correlation ($r=0.xx$, $p=0.xx$)” A legend will include the axis units. The Scatterplot matrix will be repeated twice in the same figure file for HA and NA specific ASC expression.]

- Figure 23:** Correlation of A/Shanghai/2/2013 (A/H7N9)-Specific Antibody Secreting Cells at Day 8 Post Vaccination 2 with Antibody Response at Day 21 Post Vaccination 2, Per Protocol Population
- Figure 24:** Correlation of A/Hong Kong/125/2017 (A/H7N9)-Specific Antibody Secreting Cells at Day 8 Post Vaccination 1 with Antibody Response at Day 21 Post Vaccination 1, Per Protocol Population

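### SAP Figures 10 and 11 put a HAI–Neut Spearman correlation pooled over all arms on each arm's own figure file, so 48 of the 56 panels per figure carry an r and p that are not that arm's

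*SAP*

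**What the plan says.** Protocol Section 11.6.3 says only that the correlation between HAI and Neut titers will be evaluated. It gives no method and no rule on pooling.

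SAP Section 8 supplies the rule: "The spearman correlation between HAI and Neut antibody titers will be calculated at each time point over all groups".

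The implementation note for Figure 10 (SAP Appendix 2, Section 14.2.2.1) sets the layout: "seven figure files (one for each study group, and one for overall) each with 8 separate panels". The eight panels are four visits (baseline, Day 22 post vaccination 1, Day 22 post vaccination 2, Day 181 post vaccination 2) by two strains. On the statistic it says: "The spearman correlation should be calculated over all subjects and annotated within each panel", as an r and a p. The title describes the display as by study day and study group. Figure 11 repeats the format for the per protocol population.

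The note contains two sentences on symbols that fit different layouts: "Each study group should have a unique color and marker shape used within its individual figure file", and "Within each panel distinct marker types and colors should be used to indicate the study groups". The first describes a file holding one arm; the second makes sense only where all arms share a panel.

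**The concern.** A correlation printed inside a scatter plot is read as describing the points in that plot. Here the plot holds one arm and the number describes six. A reader comparing regimens would find identical values on every arm's file and could take that as evidence that assay agreement does not depend on the regimen, when it is one calculation printed six times. The p-value has the same fault, because it reflects the pooled sample size.

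There is a second, conditional effect. The arms differ by design in priming strain, boost formulation and interval, and SAP Section 8.3.2 models these as effects on titer. If both assays rise together from one regimen to another, a pooled rank correlation counts that as agreement between assays, over and above agreement among subjects given the same regimen. No other SAP text provides a within-arm HAI–Neut correlation against which this could be seen.

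**Working it through.** The documents state no correlation value, target or power for this analysis, so there is no figure of theirs to reproduce. The check is a reading of the text, a count, and an illustration under stated assumptions.

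**1. Which subjects.** Taken alone, 'all subjects' in the Figure 10 note might mean all subjects shown in the panel. Section 8 closes that reading: the correlation "will be calculated at each time point over all groups".

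**2. Panels affected.**
- Files: 6 single-arm + 1 overall = 7.
- Panels per file: 4 visits × 2 strains = 8.
- All panels: 7 × 8 = 56. Single-arm panels: 6 × 8 = 48.

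Figure 11 has the same count. It is produced only if the per protocol trigger in SAP Section 8 (more than 10% of subjects with excluded data) is met.

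**3. Effect on the p-value.** Protocol Section 11.4.3 gives 30 subjects per arm and 180 in total. The approximate |r| needed for two-sided p<0.05 is t/√(n − 2 + t²), where t is the 97.5th percentile with n − 2 degrees of freedom.
- n = 30: t = 2.048, so 2.048/√(28 + 4.195) = 0.361.
- n = 180: t = 1.973, so 1.973/√(178 + 3.894) = 0.146.

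Precision changes in the same way. For r = 0.6, the Fisher-z 95% interval, tanh(atanh(0.6) ± 1.96/√(n − 3)), is 0.31 to 0.79 at n = 30 and 0.50 to 0.69 at n = 180.

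**4. Effect on r itself.** This was simulated with 2,000 trials per scenario, six arms of 30. The following are assumptions, not figures from the documents: log2-titer SD 1.5, lowest arm centred at 1:40, and equal arm shifts on both assays. Titers were reduced to two-fold dilutions with values below 10 set to 5, following SAP Section 4.5.2. Entries are mean pooled r v mean within-arm r.

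| Latent within-arm correlation | No arm difference | 4-fold, three arms v three | Arm means spread over 0–4 log2 |
|---|---|---|---|
| 0 | 0.00 v 0.00 | 0.31 v 0.00 | 0.44 v 0.00 |
| 0.3 | 0.28 v 0.27 | 0.50 v 0.27 | 0.60 v 0.27 |
| 0.6 | 0.56 v 0.55 | 0.70 v 0.55 | 0.76 v 0.55 |
| 0.8 | 0.75 v 0.75 | 0.83 v 0.75 | 0.87 v 0.75 |

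At zero within-arm correlation and a 4-fold difference, the pooled p was below 0.05 in 99% of simulated trials. The gap narrows as within-arm correlation rises and all but vanishes when arms do not differ.

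**5. Where arms can differ.** At baseline, randomized A/H7-naive arms should not. At Day 22 post vaccination 1, Arms 1–3 have had one identical product and Arms 4–6 another (Protocol Table 1), so there are at most two underlying means; the three-v-three column has that structure. Only after the second vaccination can all six differ.

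**The case against.** The best defence is that this is a drafting slip. The sentence about distinguishing groups within each panel fits only the overall file, which suggests a single-figure template stretched to seven files, with the pooled r meant for the overall one. The sample figures are not visible in the text available, so intent cannot be settled. That is fair, but it explains the instruction without changing what a programmer would do with it.

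It is also fair that little hangs on the display. Figures 10 and 11 are not marked for the topline set, SAP Section 6.8 says no specific null hypothesis is tested, each arm's points are plotted, and individual titers appear in Listing 9. This limits the severity.

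Three stronger readings are tempting, and the documents do not support them.

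- **That the antibody-secreting-cell figures (18–25) are mislabelled too.** Their notes also say "The spearman correlation should be calculated over all subjects", but each is a single figure showing all groups, so a pooled r belongs to what is plotted. The assay is also run only on subjects from two named locations (SAP Section 8.3.3). If these count as one of five equally enrolling sites (an assumption), that is 180/5 = 36 subjects, or 36/6 = 6 per arm, too few for useful arm-level correlations.
- **That pooling will generally create a large correlation from nothing.** With zero within-arm correlation and six evenly spaced arm means 1 SD apart (27 per arm), the pooled r averages 0.76. But that spacing cannot arise at baseline or at Day 22 post vaccination 1, and nothing in the documents supports zero correlation between the two assays within an arm.
- **That the pooled coefficient is invalid and must give way to a partial one.** A pooled r over the full titer range is a legitimate description of concordance if labelled as such, and no document promises an arm-adjusted estimate.

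**Conclusion.** The point holds for Figures 10 and 11. As written, 48 of 56 panels per figure carry an r and p that are not those of the arm shown, and the p reflects about 180 subjects instead of about 30. This rests on the SAP text alone and needs no assumption about the data.

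The distortion of r by between-arm differences is conditional. It arises only where arms differ in the same direction on both assays, which is plausible after vaccination and not expected at baseline. For an assumed 4-fold difference between two sets of three arms, it runs from 0.31 v 0.00 at zero within-arm correlation to 0.83 v 0.75 at a latent correlation of 0.8.

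Severity is minor. The display is descriptive, and no primary endpoint or sample-size figure is affected.

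**What to change.** 1. **Arm files of Figures 10 and 11.** Print that arm's own Spearman r, n and 95% CI in each panel; if a p is kept, compute it from the same subjects. Where all titers on either assay are tied, print 'not estimable'. This is likely at baseline: SAP Section 8.3.1 expects little or no pre-existing antibody, Section 4.5.2 sets values below 1:10 to 5, and a rank correlation is undefined when one variable is constant.
2. **Overall file.** Keep the pooled r, labelled as pooled over all study groups. An arm-adjusted (partial) Spearman beside it would be useful but is optional.
3. **SAP Section 8.** Amend the sentence on the HAI–Neut correlation to say that it is calculated at each time point within each group, and also over all groups for the overall figure.
4. **Figure 10 note.** Restrict the sentence on distinguishing groups within a panel to the overall file.
5. **Figures 18–25.** Label the printed r as pooled. No other change is needed.

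The cost is a few lines of SAP text and a by-group run of a calculation already planned. No new data are needed.

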14.2.2.2 Antibody Secreting Cell Figures

Figure 12: Box Plots of IgA Antibody Secreting Cells by A/H7N9 Strain, Study Day and Study Group, Modified Intent-to-Treat Population

[Implementation Note: A generic sample figure is shown below. The box plots should be presented in a single figure with 4 separate panels (2 columns for each visit (Day 8 post vaccination 1 and Day 8 post vaccination 2) and 2 rows for the strains (A/Shanghai/2/2013 (A/H7N9), A/Hong Kong/125/2017 (A/H7N9))). Visit labels should be included in the panel header. Within each panel distinct marker types and colors should be used to indicate the study groups, with study group labels included in a legend. Each study group should have a unique color and marker shape.]

[figure not shown]
Boxes indicate the 25th and 75th percentiles with the center line indicating the median. Whiskers extend to the 2.5th and 97.5th percentiles. To better visualize the results, the y-axis is presented on a log₂ scale and percent responses =0 are replaced with 0.0001.

Figures with similar format:

- Figure 13: Box Plots of IgA Antibody Secreting Cells by A/H7N9 Strain, Study Day and Study Group, Per Protocol Population**
- Figure 14: Box Plots of IgG Antibody Secreting Cells by A/H7N9 Strain, Study Day and Study Group, Modified Intent-to-Treat Population**
- Figure 15: Box Plots of IgG Antibody Secreting Cells by A/H7N9 Strain, Study Day and Study Group, Per Protocol Population**
- Figure 16: Box Plots of IgM Antibody Secreting Cells by A/H7N9 Strain, Study Day and Study Group, Modified Intent-to-Treat Population**
- Figure 17: Box Plots of IgM Antibody Secreting Cells by A/H7N9 Strain, Study Day and Study Group, Per Protocol Population**

Figure 18: Correlation of A/Shanghai/2/2013 (A/H7N9)-Specific Antibody Secreting Cells by Immunoglobulin Type at Day 8 Post Vaccination 1, Per Protocol Population

[Implementation Note: A generic sample figure is shown below. The scatter matrix should be presented in a single figure with as shown below. Within each panel distinct marker types and colors should be used to indicate the study groups, with study group labels included in a legend. Each study group should have a unique color and marker shape. The spearman correlation should be calculated over all subjects an included in the top-right diagonal as “Spearman Correlation (r=0.xx, p=0.xx)” A legend will include the axis units. The Scatterplot matrix will be repeated twice in the same figure file for HA and NA specific ASC expression.]

Figures with similar format:

- Figure 19:** Correlation of A/Shanghai/2/2013 (A/H7N9)-Specific Antibody Secreting Cells by Immunoglobulin Type at Day 8 Post Vaccination 2, Per Protocol Population
- Figure 20:** Correlation of A/Hong Kong/125/2017 (A/H7N9)-Specific Antibody Secreting Cells by Immunoglobulin Type at Day 8 Post Vaccination 1, Per Protocol Population
- Figure 21:** Correlation of A/Hong Kong/125/2017 (A/H7N9)-Specific Antibody Secreting Cells by Immunoglobulin Type at Day 8 Post Vaccination 2, Per Protocol Population
- Figure 22:** Correlation of A/Shanghai/2/2013 (A/H7N9)-Specific Antibody Secreting Cells at Day 8 Post Vaccination 1 with Antibody Response at Day 21 Post Vaccination 1, Per Protocol Population

[Implementation Note Update: The scatter matrix should be presented in a single figure with one column for each Immunoglobulin type (IgM, IgG, IgA) and one row for each antibody titer (HAI, Neut). Within each panel distinct marker types and colors should be used to indicate the study groups, with study group labels included in a legend. Each study group should have a unique color and marker shape. The spearman correlation should be calculated over all subjects an included in the top-right diagonal as “Spearman Correlation ($r=0.xx$, $p=0.xx$)” A legend will include the axis units. The Scatterplot matrix will be repeated twice in the same figure file for HA and NA specific ASC expression.]

- Figure 23:** Correlation of A/Shanghai/2/2013 (A/H7N9)-Specific Antibody Secreting Cells at Day 8 Post Vaccination 2 with Antibody Response at Day 21 Post Vaccination 2, Per Protocol Population
- Figure 24:** Correlation of A/Hong Kong/125/2017 (A/H7N9)-Specific Antibody Secreting Cells at Day 8 Post Vaccination 1 with Antibody Response at Day 21 Post Vaccination 1, Per Protocol Population
- Figure 25:** Correlation of A/Hong Kong/125/2017 (A/H7N9)-Specific Antibody Secreting Cells at Day 8 Post Vaccination 2 with Antibody Response at Day 21 Post Vaccination 2, Per Protocol Population

14.3.1.1 Solicited Adverse Events

Figure 26: Maximum Severity of Solicited Systemic Symptoms per Subject by Day Post Study Vaccination

[Implementation Note: A Generic figure is shown below. A horizontal bar chart should be presented in 6 image files (one per study group) with separate panels for each study vaccination (2 columns for vaccination #). Axes should be labeled as follows: x-axis label: Study Day, y-axis label: Percentage of Subjects (%). Study vaccination should be indicated in the panel headers including “(N=X)”, where N = the number of subjects in the Safety Population who received the relevant study vaccination. Subjects are counted at most once at the maximum severity across all systemic events reported for the specified time point]

[figure not shown]

[figure not shown]
Figure with similar format:

Figure 27: Maximum Severity of Solicited Local Symptoms per Subject by Day Post Study Vaccination

14.3.1.2 Unsolicited Adverse Events

Figure 28: Frequency of Unsolicited Adverse Events by MedDRA® System Organ Class and Severity

[Implementation Note: A Generic figure is shown below. This figure includes all unsolicited events across all doses. A horizontal bar chart should be presented in 3 image files (one per vaccination, and one for all vaccinations) with separate panels for each study groups (6 columns (study groups)). Axes should be labeled as follows: y-axis label: System Organ Class, y-axis label: Number of Events. The study groups should be indicated in the panel headers including “(N=X)”, where N = the number of subjects in the Safety Population. The y-axis should present all SOCs reported by at least 1 subject and an “All Events” category. Y-axis should be sorted with “All Events” first, then in decreasing order of total incidence]

Figures with similar format:

Figure 29: Frequency of Unsolicited Adverse Events Within 21 Days Post Dose by MedDRA® System Organ Class and Severity

Figure 30: Incidence of Unsolicited Adverse Events by MedDRA® System Organ Class and Severity

[Implementation Note: A Generic figure is shown below. This figure includes all unsolicited events across all doses. A horizontal bar chart should be presented in 3 image files (one per vaccination, and one for all vaccinations) with separate panels for each study group (6 columns). Axes should be labeled as follows: y-axis label: System Organ Class, x-axis label: Percentage of Subjects (%). The study groups should be indicated in the panel headers including “(N=X)”, where N = the number of subjects in the in the Safety Population. Subjects are counted at most once at the maximum severity across for any events in the applicable SOC. The y-axis should present all SOCs reported by at least 1 subject and an “All Events” category. Y-axis should be sorted with “All Events” first then in decreasing order of total incidence]

[figure not shown]

Figure with similar format:

Figure 31: Incidence of Unsolicited Adverse Events Within 21 Days Post Dose by MedDRA® System Organ Class and Severity

Figure 32: Frequency of Adverse Events by MedDRA® System Organ Class and Relationship to Study Vaccination

[Implementation Note: A generic sample figure is shown below. This figure includes all unsolicited events across all doses. A horizontal bar chart should be presented in 1 image file with separate panels for each study group and study dose (6 columns (study groups)). Axes should be labeled as follows: y-axis label: System Organ Class, y-axis label: Number of Events. The study groups should be indicated in the panel headers including “(N=X)”, where N = the number of subjects in the in the Safety Population. The y-axis should present all SOCs reported by at least 1 subject and an “All Events” category. Y-axis should be sorted with “All Events” first then in decreasing order of total frequency]

[figure not shown]
[figure not shown]

Figure with similar format:

Figure 33: Frequency of Unsolicited Adverse Events Within 21 Days Post Dose by MedDRA® System Organ Class and Relationship to Study Vaccination

Figure 34: Incidence of Adverse Events by MedDRA® System Organ Class and Relationship to Study Vaccination

[Implementation Note: A Generic figure is shown below. This figure includes all unsolicited events across all doses. A horizontal bar chart should be presented in a 1 image file with separate panels for each study group (6 columns (study groups)). Axes should be labeled as follows: y-axis label: System Organ Class, x-axis label: Percentage of Subjects (%). The study groups should be indicated in the panel headers including “(N=X)”, where N = the number of subjects in the in the Safety Population. Subjects are counted at most once at the maximum relationship (related >not-related) across for any events in the applicable SOC. The y-axis should present all SOCs reported by at least 1 subject and an “All Events” category. Y-axis should be sorted with “All Events” first, then in decreasing order of total incidence across groups]

[figure not shown]
Figures with similar format:

Figure 35: Incidence of Unsolicited Adverse Events Within 21 Days Post Dose by MedDRA® System Organ Class and Relationship to Study Vaccination

